in patients undergoing major laparoscopic colorectal surgery. The primary outcome measure is analgesic requirement in oral morphine equivalents in the first 48 hours after surgery. Secondary outcome measures include postoperative analgesic requirements at various time points (within the post-anesthesia care unit, at 24 hours postop, and 72 hours postop), total opioid requirements, antiemetic requirements, postoperative pain scores, length of postoperative hospital stay, any treatment-associated adverse events related to the TAP block, and overall perioperative complications in the 30-day postoperative period after major colorectal surgery.

All groups will be counseled and asked to consent for the study at the time of their preoperative clinic visit and copy of the protocol will be provided to them. Patients undergoing laparoscopic major colorectal surgery will receive general anesthesia as the primary mode of anesthesia. A standardized preoperative non-opioid pain regimen will be utilized. Both groups will receive all routine intraoperative and postoperative analgesia as deemed appropriate by the anesthesia and primary surgical team. All patients will be prescribed scheduled non-opioid analgesics with available oral and intravenous narcotics for breakthrough pain postoperatively. The current standard of care includes a multimodal approach to pain control including the utilization of a regional field block in an effort to improve pain control and decrease postoperative opioid use. The choice of local anesthetic medication administered within the TAP block is proceduralist-dependent and variable. A wide range of medications have been utilized including bupivacaine formulations with epinephrine and dexamethasone and a long-acting sustained-release liposomal bupivacaine formulation to increase the block effects or duration. Each are considered within the standard of care and have been studied independently showing improved postoperative pain control (6); however, these two formulations have not been studied against each other to determine superiority. We propose a prospective randomized study to comparing TAP blocks with injected bupivacaine/epinephrine/dexamethasone versus liposomal bupivacaine in patients undergoing major laparoscopic colorectal surgery.

STUDY METHODS

I. Recruitment

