- a) Patients of the investigators will be recruited for this study during their preoperative outpatient appointments approximately one week before surgery. The study material packet containing the HIPAA and the informed consent form will be emailed to the patient for review. Thus, the patient will have adequate time to ask questions and consider the study prior to scheduled surgery.
- b) No emails soliciting patients outside of the outpatient clinic setting will be conducted.
- c) The patients will be contacted by the study investigators the morning of surgery at which time a signed consent will be obtained.
- d) Only patients who have provided their written consent and indicated that they have been introduced to the study prior to meeting with the anesthesiologists on the day of surgery will be able to participate.
- e) Screening during each step of the recruitment process will ensure patients comply with inclusion and exclusion criteria.

II. In the preoperative holding area:

- a) Patients will provide a detailed medical history including demographic information (e.g., age, weight, height, ethnic origin, smoking history, history of motion sickness, history of postoperative nausea and vomiting, as well as chronic analgesic usage). None of this data will be recorded until written informed consent is obtained.
- b) Standard of care multimodal analgesia medications will be administered including:
 - a. Acetaminophen oral 1000 mg
 - b. Celecoxib oral 200 mg
 - c. Gabapentin oral 600 mg (300 mg for patients over age 65)
 - d. Heparin 5000 units sq
 - e. Scopolamine patch 1.5 TD (for patients < age 65)
 - f. Intravenous fluids (lactated ringers at 30 ml/hr)
 - g. Additional analgesics may be given as needed.
- c) Written informed consent will be obtained by one of the investigators.

III. During the intraoperative period

- a) Standard anesthesia monitors will be applied: automatic blood pressure cuff, three-lead electrocardiography, capnography, and pulse oximetry will be used continuously.

- b) Choice of intraoperative anesthesia drugs will be per attending anesthesiologist preference except the addition of our standard colorectal enhanced recovery protocol which will be applied to all:
 - a. Dexamethasone 4 mg IV x 1
 - b. Metoclopramide 10 mg IV x 1
 - c. Ketorolac 30 mg IV x 1 (15 mg in patients >65 y.o., renal impairment or weighing <50 kg)

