 - d. Lidocaine 2mg/kg/hr infusion (Hold for age >65, cardiac arrhythmia, Congestive heart failure (CHF), Chronic obstructive airway disease, beta-blocker use, alpha-agonist use, abnormal electrolytes, or liver impairment)
 - e. Magnesium IV bolus 30mg/kg (over 30 minutes) then 6mg/kg/hr (Hold for age >65 y.o., cardiac arrhythmia, history of heart attack, CHF, renal impairment (SCr >1.5)
Lactated ringers at 8ml/kg/hr unless blood loss >300cc or converted to open surgery
- c) Immediately after the final laparoscopic portion and before evacuation of pneumoperitoneum, the patient will undergo randomization by one of the study staff [name] via sealedenvelope.com random number generator.
 - a. If the patient underwent a conversion from laparoscopic to open surgery, they will not be randomized
- d) The study staff performing randomization [name] will instruct the surgical technologist and circulating nurse to prepare the medication formulation of the matched study arm: either bupivacaine/epinephrine/dexamethasone or liposomal bupivacaine. This will be done while the surgeon/ block administrator are outside of the operating room.
- e) For the bupivacaine/epinephrine/dexamethasone treatment arm, a standard weight-based dose will be used. A 1 ml/kg dose of 50:50 mix of 1) bupivacaine 0.25% with epinephrine (1:200,000) and 2) bupivacaine 0.25% without epinephrine will be combined with 8mg (4mg/ml) dexamethasone.
- f) For the liposomal bupivacaine treatment arm, a dosing regimen as recommended on the package insert will be used. 20 ml of 133 mg/10ml (totaling 266 mg) liposomal bupivacaine (Exparel) solution will be mixed with 0.5% bupivacaine without epinephrine totaling a 1 ml/kg weight-based volume. The maximum volume of 0.5% bupivacaine co-administered with liposomal bupivacaine is 30ml or 150 mg and will not exceed a 1:2 ratio of milligram dose of bupivacaine HCl to liposomal bupivacaine. Note, liposomal bupivacaine contains 266 mg of free base bupivacaine which is the molar equivalent to 300 mg bupivacaine HCl. Thus, a 1:2 ratio would entail a maximum co-administered dose of 150 mg or 30 ml

0.5% bupivacaine without epinephrine. For patients heavier than 50 kg, saline will be added to dilute the mixture and expand the volume to 1ml/kg total volume.

g) Groups are summarized below:

Group 1	n=50	Bupivacaine with epinephrine and dexamethasone
Group 2	n=50	Liposomal bupivacaine

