- h) The bilateral laparoscopic-guided TAP block will be performed in the anterior axillary line between the costal margin and iliac crest. After the needle is passed through the skin, it is continued until 2 distinct “pops” are felt, indicating the needle pierced each of the 2 fascia layers (external oblique and internal oblique fascia). After injection of the correct plane, a smooth raised area of fluid covered by transversus abdominis muscle is seen with the laparoscope. The laparoscopic vision also assures that the preperitoneal plane is not injected and that the injection does not go intraperitoneal. The block is administered at 2 different sites on each side (4 injections total).
- i) Dose of anesthetics, analgesics, local anesthetics, and IV fluid therapy during the operation will be recorded in the anesthesia record as per standard procedure.
- j) Duration of surgery (from skin incision until closure) and anesthesia will be recorded in the anesthesia record as per standard procedure.
- k) Total opioids received will begin recording from when skin closure begins.

IV. PACU

- a) Per standard care, verbal rating scale (VRS) for pain will be assessed by the PACU RN upon arrival to recovery room, as needed while in PACU, and then before discharge from the PACU.
- b) Narcotic usage will be tracked through PACU as a separate category
- c) Requirements for “rescue” analgesic medication will be recorded before discharge.
- d) Any adverse events during the perioperative period will also be noted by PACU RN.

V. Following completion of surgery (post-operative):

- a) Anesthesia will be discontinued at skin closure.
- b) Patients will be transferred to the recovery room after emergence from sedation
- c) Treatment of surgical pain prior to discharge from the recovery room per Standard Care:
- i. Mild pain (VRS 1-3): No rescue pain medications will be administered
 - ii. Moderate pain (VRS 4-6): tramadol 5 mg oral or hydromorphone 0.2 mg IVP every two hours if unable to tolerate oral

- iii. Severe pain (VRS 7-10): tramadol 10 mg oral or hydromorphone 0.5 mg IVP every two hours if unable to tolerate oral
- d) Patient nausea, vomiting, or retching will be initially treated metoclopramide 10 mg IV. Patients unresponsive to this will be given ondansetron 4 mg IV and prochlorperazine 10 mg IV if still ineffective, per standard care.
- e) Patient discharge criteria from PACU will include: awake and alert, and stable vital signs.

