 - a) Defined as walking >50 feet out of the patient room
- g) Physical signs and symptoms related to the peripheral nerve block (residual sensory blockade) will be noted.

VII. Post-Discharge

- a) If patient is discharged before 72 hours, they will be called by study team member and asked about their narcotic usage and timing and total narcotic use at 72 hours will be calculated
- b) If unable to be reached within 24-48 hours, they will be queried at their post-operative visit.

VIII. Adverse events

- a) If patient was converted from laparoscopic to open surgery, they will not meet criteria for randomization
- b) If a patient is readmitted to the emergency department or the inpatient hospital post-discharge within 30 days, the Clavien-Dindo classification (7), circumstances, cause, and possible associations to treatment intervention will be recorded.
- c) If a patient leaves against medical advice, they will be classified as “lost to follow-up.”
- d) The patient will be assessed in clinic at 30 days to evaluate any adverse events during this time.

Statistical Considerations

The following data will be analyzed:

- I. Data to be collected will include the following:
 - a. Demographic details
 - i. Age
 - ii. Gender

- iii. Ethnicity
- iv. Smoking/alcohol use
- v. Narcotic use
- b. Physical factors
 - i. Height
 - ii. Weight
 - iii. Body mass index
- c. Medical history -
 - i. Charlson comorbidity index (8)
- d. American Society of Anesthesiologists Classification
 - i. I – Healthy patient
 - ii. II – Patient with controlled co-existing disease(s)
 - iii. III – Patient with non-controlled co-existing disease(s)
 - iv. IV – Patient with co-morbid condition(s) that are a constant threat to life
 - v. V – Patient not expected to survive surgery
- e. Operative factors
 - i. Operative indication
 - ii. Operation received
 - iii. Conversion to open surgery
 - iv. Operation time
 - v. Incision length will be measured and tabulated by surgeon
 - vi. Number of laparoscopic ports
- f. Treatment received
- g. Outcomes
 - i. Narcotic usage
 - ii. Pain scale
 - iii. Time till flatus/ bowel movement
 - iv. Foley removal
 - v. Ambulation
 - vi. Hospital length of stay
 - vii. Adverse events
 - viii. Hospital readmission

Data Analysis

Sample size calculation:

With a sample size of 50 patients in each arm, a two group 0.05 two-sided t-test will have 80% power to reject the null hypothesis that the two groups are equivalent in morphine (mg)

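### The named primary test adjusts for neither pre-randomisation intraoperative opioid nor operation received, so the trial forgoes a possible gain in precision

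*Combined protocol and SAP*

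**What the plan says.** The combined protocol and SAP gives these elements.

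- **Endpoint** (Study Design): "The primary outcome measure is analgesic requirement in oral morphine equivalents in the first 48 hours after surgery".
- **Intraoperative drugs** (Study Methods, III.b): "Choice of intraoperative anesthesia drugs will be per attending anesthesiologist preference", apart from a fixed enhanced recovery list that applies to everyone and names no opioid. Study Design adds: "Both groups will receive all routine intraoperative and postoperative analgesia as deemed appropriate by the anesthesia and primary surgical team". In the preoperative holding area (II.b), "Additional analgesics may be given as needed".
- **Randomisation** (III.c): "Immediately after the final laparoscopic portion and before evacuation of pneumoperitoneum, the patient will undergo randomization".
- **Recording** (III.i): "Dose of anesthetics, analgesics, local anesthetics, and IV fluid therapy during the operation will be recorded in the anesthesia record".
- **Start of the opioid count** (III.k): "Total opioids received will begin recording from when skin closure begins".
- **Data to be analysed** (Statistical Considerations, I.e): the operative factors include indication, operation received and operation time, but not intraoperative opioid.
- **Test** (Data Analysis, sample size calculation): "a two group 0.05 two-sided t-test". This is the only analysis named for the primary endpoint. No covariate, regression model or stratification factor is given; allocation uses blocks of 4 and 8 only.

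**The concern.** Randomisation comes unusually late, after most of the anesthetic has been given. By then each patient has received an opioid dose that was not standardised, and its effect may carry into recovery and change early postoperative need. The operation performed may also influence 48-hour use. Opioid given before randomisation cannot be altered by allocation, so it is a legitimate baseline covariate. It is already written down for every patient.

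The t-test leaves in its error term any outcome variation that these two variables explain. With 100 patients, a chance imbalance in them moves the unadjusted estimate, whereas a linear model would remove the linear part of that shift. What is at stake is the width of the confidence interval and some power. The adjustment has to be written down beforehand, because covariates chosen after the data are seen are open to challenge.

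**Working it through.** **Inputs.** From the sample size table: difference 15, common SD 25, two-sided alpha 0.05, 50 per arm, stated power 80%. The accompanying sentence gives the difference as 50%; I use the table's 15. The documents give no correlation between pre-randomisation opioid, or operation, and 48-hour use. The share of within-arm variance explained, R², is therefore an assumption, shown from zero upward.

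**1. The plan's own figure.** The standard error of the difference is 25 × √(2/50) = 5.00. The noncentrality is 15/5 = 3.00 on 98 degrees of freedom, which gives 84.4% power by the noncentral t. The stated 80% needs only 45 per arm (44 by the normal approximation). The figure of 50 is therefore not reproduced exactly; that is a separate matter, and it errs on the safe side. The unadjusted 95% half-width is 1.984 × 5.00 = 9.9 mg.

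**2. Cost of adjustment.** One term for the dose and up to two for three operation categories make k = 3. The residual degrees of freedom fall from 98 to 95. Chance imbalance in k roughly normal covariates inflates the variance of the adjusted difference by about 1 + k/(N − k − 3) = 1 + 3/94 = 1.032, with N = 100.

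**3. Adjusted precision.** SE = 5.00 × √((1 − R²) × 1.032); half-width = 1.985 × SE; power from the noncentral t with noncentrality 15/SE on 95 degrees of freedom.

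| Assumed R² | Power, cost ignored | SE, cost charged | Half-width (mg) | Power, cost charged |
|---|---|---|---|---|
| 0% | 84.4% | 5.08 | 10.1 | 83.2% |
| 5% | 86.2% | 4.95 | 9.8 | 85.1% |
| 10% | 87.9% | 4.82 | 9.6 | 86.9% |
| 20% | 91.3% | 4.54 | 9.0 | 90.5% |
| 30% | 94.4% | 4.25 | 8.4 | 93.7% |

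Break-even is where (1 − R²) × 97/94 = 1, that is R² = 3/97, about 3%.

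**4. Opioid dose alone.** With one covariate, correlation r, and its small cost ignored, the residual SD is 25 × √(1 − r²). Power is 84.7% at r = 0.1, 85.8% at 0.2, 87.6% at 0.3, 90.0% at 0.4 and 92.9% at 0.5. At r = 0.2 or below the gain is under 2 points.

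**5. Chance imbalance.** If the covariates explain 20% of variance, an imbalance of 1.96 standard errors in them shifts the unadjusted estimate by 1.96 × √0.20 × 5.00 = 4.4 mg; at 5% the shift is 2.2 mg. The unadjusted standard error of 5.00 already allows for such shifts.

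**6. Would counting the earlier dose in the endpoint help?** Suppose, for illustration, that the dose has SD 15 and correlation 0.2 with later use. The SD of the sum is √(25² + 15² + 2 × 0.2 × 25 × 15) = √1000 = 31.6, and power falls to 65%. Only a sufficiently negative correlation avoids a loss: with dose SD 15, r = −0.3 just restores an SD of 25.

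**The case against.** The strongest reply is that no defect of known size has been shown. The documents give no correlation, name no intraoperative opioid, and offer nothing to show that a dose given during surgery influences consumption over a full 48 hours. The direction is also unclear: carry-over would lower later need, whereas a larger operation could raise both doses, and the two could offset each other. The fixed non-opioid regimen and the exclusion of chronic opioid users already limit variation. The SD of 25 is not described as net of any covariate, so it may already contain this variation. Finally, operation received has no categories in the documents and no opioid conversion is given, so the adjustment is more work than copying one number.

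Most of this stands. The size is conditional, the gain may be close to nil, and the practical cost is real. It does not remove the point. Linear adjustment works whichever sign the correlation has, and having operation in the model helps separate the two opposing influences. The worst case is a loss of about 1 point of power.

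A reader might also infer that discretionary dosing biases the comparison. The documents do not support that: randomisation follows these doses, so they balance in expectation, and the t-test remains valid.

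**Conclusion.** The point holds as a forgone opportunity and is a desirable refinement, not a required correction. Two variables that are known or obtainable for every patient could be used to sharpen the primary comparison, and the plan does not use them. With three terms charged, the effect on power runs from a loss of about 1 point (84.4% to 83.2%) if they explain nothing to a gain of about 9 points (to 93.7%) if they explain 30% of variance, with break-even near 3%. This rests on the plan's difference of 15 and SD of 25, a linear relation, and R² values that are assumed and pool dose with operation.

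Two further inferences go too far. The trial is not shown to be underpowered on this account, since the unadjusted test has 84.4% power on the plan's inputs against a stated 80%. Nor is it an error to leave pre-randomisation opioid out of the count: the endpoint concerns use after surgery, the block cannot affect an earlier dose, and adding that dose would usually raise the variance.

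**What to change.** - In Statistical Considerations, I.e (operative factors), add intraoperative opioid from induction to randomisation, in oral morphine equivalents, using one prespecified conversion.
- Prespecify the primary analysis as a linear model of 48-hour opioid use on arm, that dose, and operation received in two or three categories defined in advance.
- Keep the unadjusted t-test as a sensitivity analysis.
- State that opioid given after randomisation is not a covariate. This includes opioid given between randomisation and the start of skin closure, which the current count also leaves out; the plan should say whether that interval is to be counted.

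**Cost.** Analysis wording, plus extracting and converting each patient's doses from the existing anesthesia record up to the randomisation time, which must be available for each patient. No change to treatment or sample size. The statistical downside is about 1 point of power if the covariates explain nothing.

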- f) Postoperative enhanced recovery pathway will be initiated and multimodal analgesia will be ordered per our standard practice for all patients:
 - i. Regular diet + Boost TID starting POD 0
 - ii. Heparin 5000 units SQ TID starting POD 0
 - iii. Ambulation TID will be encouraged beginning POD 0
 - iv. Gabapentin 160 mg po QHS or 300 mg po qHS for patients over age 65
 - v. Acetaminophen 1000 mg oral every 8 hours
 - vi. Celecoxib 200 mg oral bid
 - vii. Breakthrough pain will be controlled as follows:
 - 1. Mild pain (VRS 1-3): No rescue pain medications will be administered
 - 2. Moderate pain (VRS 4-6): tramadol 5 mg oral or hydromorphone 0.2 mg IVP every two hours if unable to tolerate oral
 - 3. Severe pain (VRS7-10): tramadol 10 mg oral or hydromorphone 0.5 mg IVP every two hours if unable to tolerate oral
 - 4. Patients having pain further uncontrolled by above methods will be allowed to deviate from protocol to achieve satisfactory pain control deemed appropriate by treating physicians including but not limited to use of oral oxycodone, intravenous acetaminophen, ketorolac, patient controlled analgesia, and repeat of TAP block or epidural analgesia
 - 5. Patients matched in both control and experimental arms who require a repeat TAP block or epidural anesthesia to achieve satisfactory pain control will remain in their previously designated study group and will undergo to intention-to-treat analysis.

VI. Patient evaluation during hospital admission and up to 1 week postop:

- a) VRS for pain assessment will be utilized to assess pain within the first 72 hours postoperatively, per standard care, and pain scores will be recorded in the patient chart by the nursing staff as per routine CSMC protocol. The average pain scores will be calculated for study analysis.
- b) VRS scores along with dose and administration time for all opioids will be recorded, per standard care.

- c) Pain evaluation recorded by nursing staff as per standard CSMC guidelines:
 - a) Within the PACU as needed.
 - b) During admission: 12, 24, 48, and 72 hours postoperatively and as needed.
- d) Antiemetic usage will be recorded
- e) Return of bowel function
 - a) For patients with bowel continuity: time till flatus and BM will be measured by morning inquiry or stool production
 - b) For patients with ostomy/ diversion: time till obvious visual gas filling of the bag or ostomy production of succus beyond 20 ml / day
- f) Ambulation

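### As printed, the post-operative gabapentin line gives patients over 65 more drug than younger patients, the reverse of every other age rule in the protocol, and no reason is given

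*Combined protocol and SAP*

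**What the plan says.** Gabapentin is ordered at two points in the Study Methods of the combined protocol and SAP.

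- Before surgery (II.b, preoperative holding area): "Gabapentin oral 600 mg (300 mg for patients over age 65").
- After surgery (V.f.iv, enhanced recovery pathway): "Gabapentin 160 mg po QHS or 300 mg po qHS for patients over age 65".

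V.f introduces its list as standard practice for every patient, so the post-operative line covers both arms. Inclusion criterion 6 admits ages 18 to 90, so patients on either side of the age cut-off can be enrolled.

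Four other drugs carry an age rule. The scopolamine patch is limited to patients under 65 (II.b). Ketorolac falls from 30 mg to 15 mg over 65 (III.b). The lidocaine infusion and the magnesium bolus and infusion are both held over 65 (III.b).

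**The concern.** The two gabapentin lines concern the same drug and the same age cut-off, yet they adjust for age in opposite directions. Before surgery, older patients get less than the default; after it, they get more. No section gives a reason, and the rest of the protocol consistently gives older patients less of a drug or none of it.

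This is a dosing instruction that staff may follow, not background text. If the line is used as printed and is not what was intended, one or both age groups would receive the wrong scheduled dose of a co-analgesic. What is at stake is correct dosing by age in the common care given to both arms. The comparison between arms is not at issue.

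**Working it through.** The plan states no statistical figure on this point, so there is none to reproduce. The check compares the direction of each age rule.

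**Step 1. Ratio of over-65 dose to default dose for gabapentin.**

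- Pre-operative (II.b): 300 / 600 = 0.50, a halving.
- Post-operative (V.f.iv): 300 / 160 = 1.875, an increase of 87.5%.

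**Step 2. Direction of all age-based drug rules.**

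| Drug | Section | Rule for older patients | Direction |
|---|---|---|---|
| Gabapentin, pre-operative | II.b | 600 to 300 mg | less |
| Scopolamine | II.b | only under 65 | none |
| Ketorolac | III.b | 30 to 15 mg (15/30 = 0.50) | less |
| Lidocaine | III.b | held | none |
| Magnesium | III.b | held | none |
| Gabapentin, post-operative | V.f.iv | 160 to 300 mg | **more** |

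Five of the six rules give older patients less or nothing. V.f.iv is the only exception.

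**Step 3. Is there an explanation elsewhere?** The sections on background, methods, risks and data analysis contain no rationale for a higher gabapentin dose in older patients.

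**Step 4. What would restore the direction?** More than one change would do it:

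- If the default were 600 mg, as in II.b, the ratio would be 300/600 = 0.50.
- If the two age labels were exchanged (300 mg default, 160 mg over 65), it would be 160/300 = 0.53.
- If the over-65 dose were 160 mg or less, it would be at most 160/160 = 1.00.

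The document does not favour any of these strongly enough to choose.

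**The case against.** **No dose is stated twice.** One line is a pre-operative dose and the other a bedtime dose after surgery, so they need not match. That stands. A lower post-operative default is not in itself an error. It does not explain why the age adjustment changes direction.

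**The other four age rules concern other drugs.** Three of them (ketorolac, lidocaine, magnesium) also list triggers other than age. They show a pattern and do not bind the gabapentin line. This stands too: the pre-operative gabapentin line is the only close comparator. The pattern is supporting evidence.

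**The text was read from PDF by a program, and 160 could be a misreading.** This cannot be ruled out, because the post-operative dose appears only once. Against it, the line is legible list text, and 160 differs from 600 in two of its three digits. The possibility is a caveat that a look at the source would settle. It does not remove the inconsistency as printed.

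**A stronger reading is that 160 mg must be an error for 600 mg.** A reader might infer this because other per-dose amounts carry over unchanged: "Acetaminophen oral 1000 mg" and "Acetaminophen 1000 mg oral every 8 hours", "Celecoxib oral 200 mg" and "Celecoxib 200 mg oral bid", "Heparin 5000 units sq" and "Heparin 5000 units SQ TID starting POD 0", and gabapentin 300 mg over 65. The support is weak. Three of these four matches are other drugs with no age rule, and the fourth comes from the disputed line itself.

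**Conclusion.** The point holds as a minor inconsistency. As printed, V.f.iv gives patients over 65 1.875 times the default dose, against 0.50 times before surgery, with no stated reason. A dose or an age label in that line appears wrong, and the documents do not show which. This conclusion assumes that the printed text is a faithful reading of the source, and that an unexplained reversal of the protocol's own age adjustment was not intended.

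Four further inferences are tempting but not supported:

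- **A shortfall or excess in mg per night.** Any such figure presupposes which element is wrong and what dose was meant, so none is given.
- **Bias between arms or an effect on the primary outcome.** The line applies equally to both arms. V.f.iv also gives no start day or duration for gabapentin, unlike the diet and heparin lines, so its overlap with the 48-hour opioid window is not stated.
- **Harm from 300 mg over 65.** The protocol itself uses that amount pre-operatively.
- **Actual misdosing.** The documents do not show what the order set contains.

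**What to change.** Check V.f.iv, both doses and the age label, against the source protocol and the standard order set.

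- If the source differs from the text here and its over-65 dose does not exceed the default, the protocol needs no change.
- If the line is confirmed as printed, amend it so that the over-65 dose does not exceed the default. Investigators and pharmacy should set the doses; 600 mg, or 300 mg over 65, as in II.b, is one candidate. Then align the order set with the amended line.

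Adding a sentence of rationale alone would leave the reversed instruction in place and is not offered as a fix.

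The cost is one look-up, a pharmacy confirmation and at most a one-line amendment with a matching order-set edit. Sample size, randomization and analysis are unaffected.

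### Nothing in the plan keeps as-needed pain readings out of the average pain score, so a simple average would mix pain level with how often a patient was scored

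*Combined protocol and SAP*

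**What the plan says.** Postoperative pain is a secondary outcome. Study Design names it within a list ("antiemetic requirements, postoperative pain scores, length of postoperative hospital stay") and gives no summary measure, time point or test.

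The only analysis rule is in Study Methods VI.a. It covers VRS in the first 72 hours, states that "pain scores will be recorded in the patient chart by the nursing staff as per routine CSMC protocol", and ends: "The average pain scores will be calculated for study analysis".

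The readings that the chart will hold are described in two places:

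- VI.c, ward: "During admission: 12, 24, 48, and 72 hours postoperatively and as needed".
- VI.c, recovery room (PACU): "Within the PACU as needed". Section IV.a gives a fuller PACU schedule: "upon arrival to recovery room, as needed while in PACU, and then before discharge from the PACU".

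Rescue is tied to the same scale. Sections V.c and V.f.vii both state: "Mild pain (VRS 1-3): No rescue pain medications will be administered". The rescue tiers begin at VRS 4.

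Statistical Considerations lists the pain scale as an outcome and adds nothing. Data Analysis covers only the sample size and randomization for 48-hour morphine use. For patients discharged before 72 hours, VII.a provides a call about narcotic use and does not mention pain scores.

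**The concern.** An average over readings estimates average pain over time only if the timing of the readings is unrelated to the pain, or if the readings are weighted to correct for it. Four ward readings are scheduled in 72 hours, while as-needed readings have no limit. If a reading is taken as needed mainly because the patient hurts or asks for rescue, the number of readings depends on the outcome, and a few extra ones can dominate the mean. This arises even in patients who stay the full 72 hours.

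At stake is how the pain result is read beside the opioid result. Two arms with the same pain could show different averages because one was scored more often. A difference in the number of short, treated episodes could also look like a sustained difference in pain level.

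**Working it through.** The plan states no figure for average pain, so there is nothing to reproduce. The four scheduled ward readings and the VRS 4 threshold come from the protocol. Every pain value and scoring rate below is an assumption.

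**1. Sensitivity of the simple mean.** Let S be the mean of the four scheduled readings, k the number of as-needed readings and P their mean. The pooled mean is (4S + kP)/(4 + k). With S = 3:

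| k | P = 5 | P = 7 |
|---|---|---|
| 0 | 3.00 | 3.00 |
| 2 | 3.67 | 4.33 |
| 4 | 4.00 | 5.00 |
| 8 | 4.33 | 5.67 |
| 12 | 4.50 | 6.00 |

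The scheduled-only mean is 3.00 in every row.

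**2. Comparison with pain over time.** Suppose background VRS is 3, with k one-hour episodes at VRS 7, each scored once. For k = 4 the simple mean is (4×3 + 4×7)/8 = 5.0. The time-weighted mean is (68×3 + 4×7)/72 = 3.22.

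**3. Two arms that differ in brief episodes.** Let the number of episodes be Poisson with mean 2 in one arm and 5 in the other.

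- Simple means: 4.19 and 5.10, difference 0.92 before rounding of the means.
- Time-weighted means: 3 + 4×2/72 = 3.11 and 3 + 4×5/72 = 3.28, difference 12/72 = 0.17.
- Ratio: about 5.5.

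The ratio depends on the inputs:

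| Variant | Simple difference | Time-weighted difference | Ratio, about |
|---|---|---|---|
| Base case | 0.92 | 0.17 | 5.5 |
| Episodes peak at VRS 5 | 0.46 | 0.08 | 5.5 |
| One re-score at VRS 3 after each episode | 0.49 | 0.17 | 3 |
| 18 routine readings in 72 hours | 0.46 | 0.17 | 2.7 |
| 18 routine readings plus re-scores | 0.34 | 0.17 | 2 |
| Two-hour episodes, scheduled readings may fall inside them | 1.02 | 0.33 | 3 |
| Four-hour episodes, same | 1.12 | 0.67 | 1.7 |

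**4. Identical pain, different scoring frequency.** Hourly VRS was simulated for 72 hours in 40,000 patients per setting: patient means centred on 3 with SD 1, within-patient SD 1.8, hour-to-hour correlation 0.6, values rounded and held to 0–10. An as-needed reading was taken with a fixed probability in any hour with VRS 4 or more. The true mean is 3.06 throughout.

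| Probability | As-needed readings per patient | Pooled mean | Scheduled-only mean |
|---|---|---|---|
| 0 | 0 | 3.06 | 3.06 |
| 0.10 | 2.9 | 3.62 | 3.06 |
| 0.25 | 7.3 | 3.99 | 3.05 |
| 0.50 | 14.5 | 4.27 | 3.07 |

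If one arm were scored at 0.10 and the other at 0.25, identical pain would show a difference of 3.99 − 3.62 = 0.37.

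**5. Direction of the effect on an arm difference.** A further simulation, again with assumed variation between patients, gave:

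- Equal scoring rates: pooled difference 0.69 against a true 0.68.
- Unequal rates: a false difference of 0.34 where there was none, a true 0.67 shrunk to 0.35, or a true 0.63 raised to 0.98.

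**The case against.** **Pooling is not stated.** A reader might infer that the plan prescribes a pooled average. No sentence does. The plural in VI.a could mean an average across patients at each scheduled time. This stands, and limits the point to saying that nothing keeps as-needed readings out. If per-time averages are intended, the same clarifying sentence settles it before data are seen.

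**As needed is undefined.** Charting follows institutional guidelines that are not in the documents. That the extra readings are pain-triggered is an inference from the rescue tiers, and low scores taken after rescue would soften the upward pull. This stands too, but softening does not remove the dependence on scoring frequency.

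**A five-fold bias is not shown.** A reader might take the 5.5 as the expected distortion. It belongs to one set of chosen inputs. Nor does that example manufacture an effect: both measures rise with the same episode count, and the standardised differences are nearly equal (1.59 simple, 1.60 time-weighted). With equal scoring behaviour the difference may hardly change, and with unequal scoring it can move either way. The documents do not show that scoring differs between arms.

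**Loss of power.** In the brief-episode example, relying on four snapshots cuts the standardised difference from 1.6 to about 0.38. That model has no variation between patients other than episode counts. Once such variation is allowed, the figures are 0.51 for scheduled-only and 0.52 for pooled, so this objection largely falls.

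**Low stakes.** Pain is secondary, and VI.b separately records dose and time of every opioid. That is correct, and it bounds the importance of the point.

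**Conclusion.** The concern holds as a defect in the definition of a secondary outcome. On the plain reading of VI.a with VI.c, every charted score can enter an unweighted average. If as-needed readings cluster at VRS 4 or more, that average overstates the pain level; in the simulation with identical pain, by about 0.6 points (3.62 − 3.06) to 1.2 points (4.27 − 3.06).

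The effect on the arm comparison cannot be computed from the documents. Under assumed inputs it ranges from almost none, through a stretch of about 2- to 5.5-fold when the arms differ in brief episodes, to a false or diminished difference when scoring frequency differs by arm.

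A reader might go further and conclude that the pain comparison is biased towards a particular arm, or that the trial's main conclusion is in doubt. The documents support neither. They give no arm-specific scoring pattern, and the primary outcome, 48-hour oral morphine equivalents, does not use the pain average.

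**What to change.** In VI.a, define the analysed pain outcome as the scheduled 12, 24, 48 and 72 hour VRS scores, compared at each time or as a time-weighted average over those times. With straight-line interpolation, the weights would be 6, 18, 24 and 12 hours out of 60. Then add:

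- As-needed readings stay out of the average and are reported separately, for example as the number of readings at VRS 4 or above per patient.
- PACU arrival and discharge scores form their own outcome, with VI.c brought into line with IV.a on which PACU readings are taken.
- A rule for scheduled scores missing because the patient left before 72 hours, since the VII.a call does not collect pain.

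The scheduled scores are already charted in routine care, so redefining the outcome needs no new data collection. The cost is that fewer readings per patient enter the average, with a small loss of precision. The average would also cover 12 to 72 hours only, leaving the earlier period to the PACU and as-needed summaries.
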